# 9.4 Other Safety Analysis

The incidence of worsening depressive symptoms during the treatment period will be compared between CT-152 and sham groups using Cochran-Mantel-Haenszel (CMH) General Association Test on OC dataset. Worsening depressive symptoms are defined as 1) CC 2) Any AE of worsening depression. Rates and

their 95% confidence intervals will be reported and the estimated differences between groups will be provided.

#### 9.5 Concomitant Medications

Number and proportion of patients taking concomitant medications prior to the treatment period, during the treatment period, and during the extension period are tabulated by drug classification using the World Health Organization (WHO) drug dictionary on the Safety Sample.

#### 9.6 Extent of Exposure

Duration of exposure is defined as the last day of intervention with double-blind digital therapeutic - the first day of intervention with double-blind digital therapeutic +1, during the treatment period. The number and percentage of subject who receive double-blind digital therapeutic, will be presented by week and by treatment group. Each treatment week will be based on the actual week, i.e., Day 1-7 in Week 1, Day 8-14 in Week 2, etc. Mean, range, and standard deviation of the duration of exposure will also be provided. This summary will be performed on the Safety Sample.

#### 10 Conventions

## 10.1 Study Visit Windows

Study visit windows will be used to map visits using study day intervals. Observations at each scheduled visit and Early Termination will be assigned to Week 2, Week 4, Week 6, Week 8 and Week 10 based on their visit windows as shown in Table 10.1-1. This visit window convention applies to tables and listings for all efficacy scales (MADRS, GAD-7, CGI-S, PHQ-9, WHODAS2.0, CCI, and CCI). This derived study window variable will be named as WEEK and will be footnoted. In listings it will be listed along with the eCRF study visit.

Table 10.1-1 shows classifications for study day intervals in the treatment period and extension period. The variable "target day" is defined using the number of days since the start of intervention with double-blind digital therapeutic in the treatment period. The first day of intervention with double-blind digital therapeutic is defined as "Day 1". If more than one observation falls within a particular study day interval, then the last observation within that interval is used. Assessments done during the treatment period and occurring more than seven days after the last date of the interaction with double-blind digital therapeutic in the treatment period will be excluded from efficacy analyses of the treatment period.

[figure not shown]
SAP 345-201-00002

Table 10.1-1 Study Day and Visit Windows in the Trial					
Week	Target Day a	Study Day Interval a			
2	14	2~20			
4	28	21~34			
6	42	35~48			
8	56	49-62			
10	70	63-77			

<sup>a Relative to the first day of intervention with double-blind digital therapeutic in the treatment period.

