ADT = antidepressant therapy; ATRQ = Antidepressant Treatment Response Questionnaire; CGI-S = Clinical Global Impressions-Severity; C-SSRS = Columbia-Suicide Severity Rating Scale; CCI ; DSM-5 = Diagnostic and Statistical Manual of Mental Disorders, Fifth Edition; CCI ; GAD-7 = Generalized Anxiety Disorder-7; HAM-D₁₇ = Hamilton Rating Scale for Depression, 17-item; CCI ; MADRS = Montgomery-Asberg Depression Rating Scale; M.I.N.I = Mini International Neuropsychiatric Interview; PHQ-9 = Patient Health Questionnaire-9; W = week; WHODAS = World Health Organization Disability Assessment Schedule.

Note: Shaded cells indicate trial days that subjects will be contacted by telephone by the trial site.

The screening visit may be performed in person at the discretion of the investigator.

^aThe subject's understanding of, and interest in, the trial will be demonstrated through adequate adherence to onboarding requirements. CCI

^bAfter Week 6, subjects will continue participation in the trial during the extension period (Weeks 7 to 10). In the extension period, the digital mobile applications will remain installed for each group. Subjects will receive brief SMS messages reminding subjects of the previously completed CT-152 or sham treatment courses, and will continue their ADT.

^cThe end of the trial will be Week 10.

^dAll remote visits via telemedicine technology and telephone contacts after baseline have a ± 3 day window to allow for variations in subject schedules and for weekends.

^eIf deemed necessary by the investigator, additional evaluations may also be performed at an unscheduled visit either remotely or in person.

^fFor subjects who discontinue early before Week 6, the procedures designated for Day 42 (including subject debriefing) will be obtained at an early termination visit occurring as soon as possible after the last use of CT-152 or sham.

^gFor subjects who discontinue early from the trial but after Week 6, the procedures designated for Day 70 will be obtained at an early termination visit occurring as soon as possible after the last use of CT-152 or sham.

^hElectronic informed consent may be completed the day of, or prior to, the screening visit.

ⁱAt the screening visit, ADT use should be confirmed per the eligibility criteria. For all other visits, the ADT compliance should be checked.

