All remote visits and telephone contacts after baseline will have a \pm 3 day visit window to allow for variations in subject schedules and for weekends. Every effort should be made to have the remote visit or telephone contact on the designated trial day to ensure that the overall treatment period in the protocol has been maintained. Subsequent remote visits and telephone contacts should be based on the date of the baseline visit, not the previous remote visit/telephone contact. It is suggested that telephone contacts with the subject be scheduled in advance. If advanced scheduling is not possible, and the subject is not able to be reached by telephone on the first attempt, the trial site should make 3 more attempts to contact the subject, considering alternative days to reach the subject within the designated time frame.

Protocol No. 345-201-00002

The assessments to be conducted during the trial are summarized in the schedule of assessments (Table 1.3-1). A brief summary of the assessments to be performed at each visit is provided below.

The screening procedures and data collection may be performed remotely or in person, at the discretion of the investigator, and a minimum of 7 consecutive days will be required for screening. The following information will be collected during the screening period:

- Demographic information (collection date, age, sex, race, and ethnicity).
- Medical history of significance including relevant surgical procedures. A general clinical evaluation will be performed, including concurrent medical conditions, medical history over the past 2 years, and medical history beyond 2 years that is considered to be clinically relevant per the investigator's judgment.
- Prior and concomitant medication including confirmation of ADT use per the eligibility criteria. The dose and schedule of ADT, start/stop dates, as well as whether brand or generic medication is being taken will be recorded.
- Washout from prohibited concomitant medications, if applicable, will begin after consent has been obtained (see Section 6.5.1).
- Psychiatric history and diagnosis, including description of all prior treatments for
 psychiatric disorders, start date of current episode, and number of previous episodes.
 This includes the *DSM-5* diagnosis of MDD that will be made by an adequately
 trained and experienced clinician. The M.I.N.I will be used to confirm the subject's
 diagnosis of MDD and to rule out exclusionary comorbid psychiatric disorders.

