- The baseline MADRS must be completed prior to or on the day of the baseline visit, or prior to usage of the digital therapeutic treatment following randomization. The MADRS is conducted by the blinded and independent rater and should be scheduled by the trial site staff.
- The following will be administered by the trial site staff: CGI-S and C-SSRS.
- The following will be completed by the subject: GAD-7 and WHODAS 2.0.
- Prior/concomitant therapy and AEs will be recorded.

Treatment Period

The following will be performed during the remote visits at Weeks 2, 4, and 6:

- Check of ADT compliance.
- Adherence check of the use of the digital mobile application (Weeks 2 and 4 only).
- The MADRS will be conducted by the blinded and independent rater. Except for the baseline MADRS (see above), the MADRS at other visits may occur separately from the remote trial site visit but must be performed within the window.
- The following will be administered by the trial site staff: CGI-S and C-SSRS.

Protocol No. 345-201-00002

- The following will be completed by the subject: GAD-7, WHODAS 2.0 (Week 6 only), PHQ-9 (Weeks 4 and 6 only), CCl and CCl
- The principal investigator or the clinical trial member most familiar with the subject will complete the CCl
- Concomitant medications and AEs will be recorded.

During each telephone contact by the trial site at Weeks 1, 3 and 5, concomitant medications and AEs will be recorded and an adherence check of the use of the digital mobile application will be performed.

Extension Period

The following will be performed during the remote visits at Weeks 8 and 10:

- Check of ADT compliance.
- The MADRS will be conducted by the blinded and independent rater. The MADRS at Weeks 8 and 10 may occur separately from the remote trial site visit but must be performed within the window.
- The C-SSRS will be administered by trial site staff.
- The GAD-7 will be completed by the subject.
- Concomitant medications and AEs will be recorded.

During each telephone contact by the trial site at Weeks 7 and 9, concomitant medications and AEs will be recorded.

All MADRS assessments during the trial will be conducted by the blinded and independent rater, and will be recorded. Regular quality reviews of MADRS audio recordings will be performed in order to verify the quality of the MADRS interview and accuracy of scoring. The process for data oversight will be outlined in the Site Operations Manual.

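### SAP 10.1 counts study days from first app use while the Protocol times visits from the baseline visit, and no rule stops a late starter's Week 6 rating from being labelled Week 4

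*SAP*

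**What the plan says.** **SAP 10.1 (Study Visit Windows).** The target day "is defined using the number of days since the start of intervention with double-blind digital therapeutic in the treatment period", and "The first day of intervention with double-blind digital therapeutic is defined as" Day 1. A footnote to Table 10.1-1 repeats this origin. Ratings from scheduled and early-termination visits are sorted by study day into Week 2 (2–20), Week 4 (21–34), Week 6 (35–48), Week 8 (49–62) and Week 10 (63–77). "If more than one observation falls within a particular study day interval, then the last observation within that interval is used". The convention covers all efficacy scales. The resulting variable, WEEK, is listed next to the eCRF visit, so the two are separate items. The section also excludes treatment-period assessments made more than seven days after the last app interaction in that period.

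**Protocol Section 8 (Trial Procedures).** "Subsequent remote visits and telephone contacts should be based on the date of the baseline visit, not the previous remote visit/telephone contact". Table 1.3-1 sets Weeks 2, 4, 6, 8 and 10 at Days 14, 28, 42, 56 and 70, with a plus or minus 3 "day window to allow for variations in subject schedules and for weekends".

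**Start of the app.** Protocol 6.1.1 has the intervention start on the day of the baseline visit. Section 8 also allows the baseline MADRS to be done "or prior to usage of the digital therapeutic treatment following randomization", so first use can come after that visit.

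**The concern.** The documents use two day origins, and the SAP does not say what happens when they differ. Late starts are not excluded. The FAS requires one use of the app with no deadline (Protocol 9.2), nonadherent subjects may stay in the trial (Protocol 7.3.1), and the first scheduled adherence check is the Week 1 call, nominally Day 7.

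For a late starter, every rating is labelled earlier than the visit at which it was taken. The Week 6 MADRS is the primary endpoint, so a rating moved to Week 4 leaves the primary value empty, or filled by something else. A Week 8 rating would be a poor substitute. Under Protocol 6.1.1 the EFMT and SMT exercises are no longer available in the extension, and only the CT-152 arm keeps access to psychotherapy content.

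The Week 8 and Week 10 labels shift too. They feed the durability assessment (SAP 8.2.1) and the interim efficacy rule, which requires differences above 1.6 at Weeks 6, 8 and 10 (SAP 8.6).

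**Working it through.** **Inputs.** Visit days and the 3-day window come from Protocol Table 1.3-1; week intervals and the last-observation rule come from SAP 10.1. Let d be the number of days from the baseline visit to first app use. Both documents call their own starting day Day 1, so

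study day = protocol day − d.

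**1. Same-day start (d = 0).** In-window visits fall on Days 11–17, 25–31, 39–45, 53–59 and 67–73. Each range lies inside its own interval in Table 10.1-1, so all 35 combinations (5 visits × 7 days) get the intended week. The table works as designed in this case.

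**2. Slack.** The earliest in-window Week 6 day is 39 and the interval opens at 35, so the slack is 39 − 35 = 4 days. Weeks 4, 8 and 10 give the same: 25 − 21, 53 − 49 and 67 − 63.

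**3. Late starts.**

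| d | Week 6 visits labelled Week 4 | Week 8 visits placed in the Week 6 interval | In-window days moved, per visit |
|---|---|---|---|
| 0 to 4 | none | none | 0 of 7 |
| 5 | Day 39 → 34 | Day 53 → 48 | 1 of 7 |
| 8 | Days 39–42 → 31–34 | Days 53–56 → 45–48 | 4 of 7 |
| 11 | Days 39–45 → 28–34 | Days 53–59 → 42–48 | 7 of 7 |

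At d = 8 with every visit on its target day, 28 → 20 (Week 2), 42 → 34 (Week 4), 56 → 48 (Week 6) and 70 → 62 (Week 8). Week 10 is then empty.

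**4. Literal reading of the window rule.** If m of 7 days move, the Week 6 value stays correct only when neither the Week 6 nor the Week 8 visit moves, which is (7 − m)² of 49 combinations. Week 6 is therefore missing or an extension rating in 49 − 36 = 13 of 49 at d = 5, 49 − 9 = 40 of 49 at d = 8, and 49 of 49 at d = 11. These count calendar combinations and are not probabilities.

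**5. Would the seven-day rule remove a Week 8 rating?** It is worded for assessments done during the treatment period, so it does not clearly apply. If it is applied, the answer depends on the last app use, which has to be assumed:
- last use on Protocol Day 42: gap 53 − 42 = 11 to 59 − 42 = 17 days, so the rating is excluded;
- last use on study day 42 (six weeks from first use): gap at most 48 − 42 = 6 days, so it is kept.

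**6. Other scales.** CGI-S and PHQ-9 are not collected after Week 6. A relabelled Week 6 rating therefore leaves their Week 6 value empty in MMRM and observed-case analyses. WHODAS 2.0 is analysed by ANCOVA, run primarily on LOCF data (SAP 5.2, 8.3). There the relabelled value is carried forward to Week 6 unchanged, so that analysis is unaffected.

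**The case against.** **Same-day start.** The app is activated during the baseline visit, subjects have already passed onboarding, missed sessions trigger reminders, and sites check adherence at Week 1. A delay of 8 days means missing the whole first week despite all this. This stands: only late starters are affected, and they may be few. The 5-day threshold is also an edge case, since it needs a visit exactly 3 days early and Section 8 asks for visits on the designated day.

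**Primary data limited to the treatment period.** A reader might infer that extension ratings will serve as the primary Week 6 value. The documents do not support stating that as the outcome. SAP 8.1.1.2 limits the model to scheduled treatment-period visits at Weeks 2, 4 and 6, Protocol 9.4.1.1.2 limits it to planned visits in the 6-week treatment period, and SAP 5.2 defines observed cases by scheduled visit. If these select by nominal visit, a Week 8 rating stays out. The seven-day rule may also remove it. What remains is that none of this text says whether nominal visit or derived WEEK selects the data, and SAP 10.1 points to WEEK. Even with extension ratings barred, WEEK would still label the true Week 6 rating Week 4.

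**First use is a sensible origin.** It is the SAP's reference for baseline, treatment-emergent events and exposure. If access ran six weeks from first use, a Week 8 rating at study day 48 would be close to a six-week exposure rating. That weakens the case for moving every definition to the baseline visit. It does not remove the need for one rule on efficacy windows.

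**Conclusion.** The conflict between the two origins is real, and the correction is small. As SAP 10.1 is written, a late starter's genuine Week 6 rating can be labelled Week 4: from a 5-day delay at the early edge of the window, from 8 days for on-target visits, and from 11 days for every in-window visit. Use of a Week 8 rating as the primary value is a possible reading that the SAP leaves open.

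A reader might also want a count of affected subjects. Assuming that 2% to 5% of 360 start 8 or more days late gives 7 to 18 (0.02 × 360 = 7.2; 0.05 × 360 = 18). The documents do not support that figure. They give no rate of late starts, and at d = 8 only 4 of 7 in-window days move each visit. Neither the size nor the direction of any bias in the Week 6 difference can be derived.

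The thresholds assume visits inside the Protocol window and the Day 1 convention of each document.

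**What to change.** In SAP 10.1, for post-baseline efficacy scales:

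1. Assign a rating collected at a scheduled visit within its Protocol window, counted from the baseline visit, to that nominal week.
2. Use the day windows of Table 10.1-1 only for early-termination, unscheduled or out-of-window ratings.
3. State that a rating from a nominal Week 8 or Week 10 visit cannot be assigned to Week 6.

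Nominal visit and WEEK then agree for all 35 in-window combinations at any delay, so the question of which one selects the primary data no longer matters for those ratings. Leave the baseline, treatment-emergent and exposure definitions anchored to first use.

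The cost is a few sentences, one added derivation in the analysis dataset, and a second day origin that applies to efficacy windows only. Same-day starters seen within the Protocol windows keep the labels they have now.

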7.3.2 Treatment Discontinuation

After CT-152 or sham assignment, a subject may stop CT-152 or sham permanently for a variety of reasons. Treatment discontinuations may be initiated by a subject who is not satisfied with treatment or may become medically necessary due to AEs, require treatment with a prohibited medication or therapy, or other issues, as determined by the investigator.

When a subject discontinues or is withdrawn from the trial, the investigator will perform a final assessment, including the procedures indicated in the schedule of assessments (Table 1.3-1) for Day 42 as well as subject debriefing (subjects who discontinue early before Week 6) or Day 70 (subjects who discontinue early from the trial after Week 6). The Day 42 or Day 70 procedures should be performed on the last day the subject utilizes the double-blind digital mobile application or as soon as possible after the subject discontinues in order to complete all safety and effectiveness measurements.

In the event that a subject discontinues, every effort will be made by the investigator to determine why a subject fails to return for necessary visits or is dropped from the trial to record the reasons for withdrawal as thoroughly as possible. Reasonable efforts will be made by trial site staff to retain subjects in the trial and to complete remote visits and telephone contacts. Efforts will include outreach via telephone or e-mail when a subject misses a remote visit or telephone contact and rescheduling missed remote visits and telephone contacts within the \pm 3 day visit window.

The digital mobile application on the discontinued subject's smartphone device will be uninstalled as described in Section 6.2.1.

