# 8.1.1.1 Primary Estimand

The primary estimand defining the treatment effect of interest in the protocol uses the hypothetical strategy specified in the International Council for Harmonisation (ICH) E9 Addendum. The objective of the primary analysis is to compare the efficacy of CT-152 and sham. The estimand, or target of estimation, following the hypothetical strategy is the treatment effect seen, had no withdrawals occurred. Subjects who withdraw from a CT-152 or sham either could have lost their treatment effect, had the subjects not taken any other treatment after withdrawal, or could have their treatment effect been masked, had the subjects taken other treatment after withdrawal. This means that any observations taken after subjects stop CT-152 or sham will most likely not contribute relevant information about the treatment effect. Due to this strategy, the last collected efficacy assessment after premature trial discontinuation will be done only once at the early termination (ET) visit. Every effort will be made to complete all of the ET evaluations prior to administering any other treatment. In the case of terminal or lost to follow-up events no ET evaluations would be expected, and only scheduled assessments performed before such an event has occurred.

The primary estimand for this trial is defined by the following components:

- Target population: FAS Sample
- Endpoint: change from baseline to Week 6 in the MADRS total score
- Intercurrent events: premature treatment discontinuation
- Measure of intervention effect: difference in endpoint means between CT-152+ADT and sham+ADT

In this hypothetical strategy, the event of withdrawing CT-152+ADT or sham+ADT is considered missing at random (MAR), and the primary endpoint of the trial could be considered as a combination of the measurements of on-treatment completers at Week 6 and the imputation of the endpoint to Week 6 following the trend in each treatment group using the mixed model repeated measurements (MMRM) method to impute missing data for subjects who withdraw CT-152+ADT or sham+ADT during the trial. All data collected during the trial treatment period will be used for statistical analysis. For the primary efficacy analysis, the treatment effect will be estimated using the MMRM method described below.

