## 8.1.1.2 Primary Analysis Method

The primary analysis will utilize a MMRM with an unstructured (UN) variance covariance matrix in which the change from baseline in MADRS total score at scheduled treatment period visits (Weeks 2, 4, and 6) will be the dependent variable based on the OC data set on FAS Sample. The model will include fixed class effect terms for treatment, visit, treatment by visit interaction, and site to assess heterogeneity of treatment effects. This model will also include an interaction term of visit by baseline MADRS total score as a covariate. The primary comparison between the CT-152+ADT or sham+ADT at Week 6 will be estimated as the difference between least squares means utilizing the computing software SAS procedure PROC MIXED.

The mathematical formula for the MMRM model is as follows:

$$\mathbf{y} = \mathbf{X}\boldsymbol{\beta} + Z\mathbf{u} + \epsilon$$

Where

y denotes the observed vector of change from baseline to Week 6 in MADRS total score;

X is the known matrix for the fixed effects and covariate;

 $\beta$  is an unknown fixed-effect parameter vector;

Z is the known matrix for the random effect of subject;

u is an unknown vector of random effect of subject with mean  $\mathbf{0}$  and variance-covariance matrix  $\mathbf{G}$  (unstructured covariance matrix);

 $\epsilon$  is an unknown vector of random errors with mean 0 and variance **R**.

In case there is a convergence problem with the MMRM model with the unstructured variance-covariance matrix, the following structures other than unstructured will be used in order of 1) heterogeneous toeplitz (TOEPH), 2) heterogeneous autoregressive of order 1 (ARH1), and 3) heterogeneous compound symmetry (CSH). The first (co)variance structure converging to the best fit will be used as the primary analysis. If a structured covariance has to be used, the "sandwich" estimator of the standard error of the fixed effects parameters will be used in order to deal with possible model misspecification of the covariance matrix.

Small trial sites will be defined as trial sites that do not have at least one evaluable subject (evaluable with regard to the primary efficacy variable) in each treatment arm. All small trial sites will be pooled to form "pseudo sites"

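### SAP 10.1's last-observation rule lets an early-termination rating displace a completed scheduled MADRS rating, in a narrow case even at Week 6

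*SAP*

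**What the plan says.** SAP 10.1 maps by study day: "Observations at each scheduled visit and Early Termination will be assigned to Week 2, Week 4, Week 6, Week 8 and Week 10". The treatment-period intervals are Days 2–20 (Week 2), 21–34 (Week 4) and 35–48 (Week 6). The tie-break is: "If more than one observation falls within a particular study day interval, then the last observation within that interval is used". It does not distinguish scheduled from ET ratings. The same section has one limit: treatment-period assessments "occurring more than seven days after the last date of the interaction with double-blind digital therapeutic in the treatment period will be excluded" from the treatment-period efficacy analyses.

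In the protocol's schedule (section 1.3), remote visits and "telephone contacts after baseline have a ± 3 day window", and Protocol 8.1.1 requires the MADRS within that window. Under footnotes f and g of the schedule and Protocol 7.3.2, withdrawal before Week 6 triggers the Day 42 procedures and later withdrawal the Day 70 procedures. Both include a MADRS. Protocol 7.3.2 says these procedures "should be performed on the last day the subject utilizes the double-blind digital mobile application or as soon as possible after the subject discontinues".

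On the analysis side, SAP 8.1.1.2 states that change from baseline "at scheduled treatment period visits (Weeks 2, 4, and 6) will be the dependent variable based on the OC data set on FAS Sample". SAP 5.2 describes the observed-cases (OC) data as ratings from scheduled visits. SAP 8.1.1 places the primary analysis at the last on-treatment evaluation, Week 6. SAP 8.1.1.1 says that "any observations taken after subjects stop CT-152 or sham will most likely not contribute relevant information about the treatment effect". It also plans a single ET efficacy assessment and commits to using all treatment-period data.

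**The concern.** The analysis intervals extend three days beyond the latest permitted scheduled visit. An ET rating in that space, or between an early scheduled visit and the end of the interval, counts as the last observation and takes the scheduled rating's place.

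At Week 6 the displaced value is the primary endpoint. The value that takes its place comes from the extension, when the training exercises are no longer available in either arm (Protocol 6.1.1), so it is hard to call it the last on-treatment evaluation. At Weeks 2 and 4 the displaced value helps the model predict Week 6 for subjects who drop out.

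The substitution happens only in subjects who withdraw. If the reasons for or timing of withdrawal differ by arm, the treatment difference could move.

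**Working it through.** **1. Planning figures.** SAP section 4 gives a difference of 3, SD 9, two-sided α 0.05 and 85% power. n per arm = 2 × (1.960 + 1.036)² × 9² / 3² = 161.6, so 162 per arm and 324 in total; 324 / 0.90 = 360 randomized. Both figures reproduce. The standard error of the difference is 9 × √(2/162) = 1.0, and power is 85.1%.

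**2. Days on which displacement is possible.**

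| Week | Scheduled window (±3 days) | SAP interval | ET days that displace an on-target visit | Earliest displacing ET day (visit at early edge) |
|---|---|---|---|---|
| 2 | 11–17 | 2–20 | 15–20 | 12 |
| 4 | 25–31 | 21–34 | 29–34 | 26 |
| 6 | 39–45 | 35–48 | 43–48 | 40 |

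Depending on the visit day, 9, 8, 7, 6, 5, 4 or 3 later days remain in the interval. That is 42 visit-day/ET-day pairs per week, a mean of 6 days. At Week 6 a completed scheduled rating must already exist. An ET rating from a subject who withdrew before the Week 6 visit displaces nothing at Week 6; it fills an empty interval.

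**3. The seven-day exclusion.**
- *Weeks 2 and 4:* a subject rated on Day 14 who stops the app that day and has an ET rating on Day 19 is 5 days past last use. The ET rating is kept and displaces Day 14.
- *Week 6:* the exclusion covers assessments done during the treatment period, so whether it reaches an extension-period ET rating is unclear. If it does apply, with a Day 42 visit, last use on Day 41 or 42 leaves all of Days 43–48 eligible, last use on Day 38 leaves Days 43–45, and last use on Day 35 or earlier leaves none. A Day 40 rating followed by an ET on Day 47 survives if last use was Day 40 or later (47 − 40 = 7, which is not more than seven).

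**4. How many subjects.** The documents give no dropout rate or timing. Assume dropout of 10–20% of 324 (32.4 to 64.8 subjects), spread evenly over 70 days, scheduled ratings spread evenly over ±3 days, and an ET rating for every dropout.
- *ET on the dropout day:* a mean of 6 displacing days per window, 6/70 = 8.6% of dropouts.
- *ET 0, 1, 2 or 3 days later, equally likely, with dropout on or after the visit day:* the mean loss is (0 + 0 + 1 + 2)/4 = 0.75 days, so 5.25/70 = 7.5%.
- *Week 6 rating displaced:* 32.4 × 0.075 = 2.4 to 64.8 × 0.086 = 5.6 subjects.
- *Any of Weeks 2, 4 and 6:* three times the percentage, 22.5–25.7%, giving 7.3 to 16.7 subjects.
- *If only 50–75% of dropouts have an ET rating (assumed):* Week 6 falls to 2.4 × 0.50 = 1.2 up to 5.6 × 0.75 = 4.2 subjects.

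**5. How much it could move the result.** Treating the Week 6 contrast as a difference of simple means, a share f of one arm moved by d points shifts it by f × d. Power after a shift against CT-152 is Φ((3 − shift)/1.0 − 1.96).

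| Case (one arm only, assumed) | Shift | Power |
|---|---|---|
| 1% moved 5 points | 0.05 | 83.9% |
| 2% moved 5 points | 0.10 | 82.6% |
| 4 of 162 moved 8 points | 0.20 | 80.0% |
| Both arms affected alike | 0 | 85.1% |

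**6. Alternative rules.** With scheduled-visit priority, displacement occurs in 0 of the 42 pairs at each week. With closest-to-target alone, the ET rating still wins in 5 + 3 + 1 = 9 of 42 pairs (visits three, two and one days early), with 3 ties.

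**The case against.** The plan accepts near-stop ratings on purpose. SAP 8.1.1.1 provides for one ET assessment, the protocol wants it on or soon after the last day of use, and SAP 10.1 sets a seven-day limit. A reader might infer that using an ET rating at Week 2 or 4 flatly contradicts the estimand's remark about post-stop observations. The documents do not support that: the same section goes on to plan the ET assessment and to use all treatment-period data. At Weeks 2 and 4 the rule is a poorer choice of data, not a contradiction.

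The Week 6 case also has limits. The estimand's intercurrent event is premature treatment discontinuation, and a subject who finishes six weeks and then leaves the extension has not had that event. So the tension at Week 6 is with the on-treatment evaluation and the scheduled-visit basis of the data, not with the intercurrent-event strategy. One could also read SAP 5.2 and 8.1.1.2 as keeping an extension-period ET rating out of the Week 6 model altogether. That reading is possible, but SAP 10.1 assigns ET ratings by day alone and Day 47 falls in the Week 6 interval, so the sections leave the matter open.

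The counts are generous. SAP 8.1.1.1 expects no ET rating from subjects lost to follow-up, and Protocol 7.3.4 rules out further evaluations once consent for future information is withdrawn. The rule is prespecified and the same in both arms. The per-protocol sensitivity analysis excludes subjects not treated for six weeks, which covers the Week 2 and 4 cases but not the Week 6 one.

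These points reduce the size of the concern. None of them supplies a priority rule or a reason to overwrite a valid scheduled rating.

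**Conclusion.** The point holds as a minor one. Applied as written, SAP 10.1 can displace a completed scheduled rating: at Weeks 2 and 4 when the ET rating is within seven days of last use, and at Week 6 when a subject completes that visit and has an ET rating by Day 48. The Week 6 case is inconsistent with a primary analysis at the last on-treatment evaluation and with the scheduled-visit basis of the OC data and the primary model.

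A reader might infer that withdrawal ratings routinely replace the primary endpoint, or that the primary result is biased. Neither follows. Withdrawals before the Week 6 visit leave no Week 6 rating to displace. Under the assumptions in the working, about 2 to 6 of 324 subjects would be affected at Week 6, and fewer once dropouts without an ET rating are removed. The one-sided extreme is about 0.2 points, one fifth of the planning standard error, and the shift is zero if the arms are affected alike. Dropout rate, timing, ET completion and score change are all assumed, so the actual effect cannot be fixed from the documents. The planned sample size is unaffected.

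**What to change.** In SAP 10.1, replace the last-observation rule with these provisions:

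- If an interval contains a scheduled-visit rating, use it; if there is more than one, use the one closest to the target day.
- Use an ET or unscheduled rating only when the interval has no scheduled rating.
- A rating made in the extension period may not replace an existing scheduled Week 6 rating.
- List the ET ratings that are not used.

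The scheduled-visit priority must come first, because closest-to-target alone does not remove the problem (step 6 of the working). The same edit should state whether the seven-day exclusion applies to an ET rating made after the Week 6 visit, and align the OC definition in SAP 5.2 with the mapping of ET ratings.

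The cost is a few sentences and a small programming change. The downside is that a few ET ratings appear only in listings; ET ratings still fill otherwise empty intervals.
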